9.11.2.7. Sensitivity Analyses

Sensitivity analyses will also be conducted to examine the extent to which changes in certain methods or assumptions affect the results. The following sensitivity analyses are planned:

- As described in Section 9.11.1.1.3, a sensitivity analysis will be conducted that applies a stricter definition of prospective enrollment. For this analysis, individuals who enroll or make initial contact with the registry prior to diagnostic prenatal testing (and prior to pregnancy outcome) will be considered prospectively enrolled, and individuals who enroll or make initial contact with the registry after diagnostic prenatal testing, regardless of the results, will be considered retrospectively enrolled in addition to individuals who enroll after pregnancy outcome. The outcomes of individuals who enroll prior to diagnostic prenatal testing will be compared with those of individuals who enrolled after diagnostic prenatal testing.
- As described in Sections 9.11.1.1.6 and 9.11.1.1.7, additional pregnancies within the same participant are excluded from the analysis population and multiple gestations are excluded from certain calculations. The assumption is that both scenarios will be relatively rare. However, if 10% or more of the participants have more than 1 pregnancy in the registry or if 10% or more have multiple gestation pregnancies, a corresponding sensitivity analyses of all outcomes of interest will be conducted that account for the correlation between previous and subsequent pregnancies in the same participant and multiple gestation pregnancies using mixed models. If percentage is less than 10%, attempting to model the correlation will likely result in a failure of model convergence.¹⁰⁶

- To test the robustness of the IPTW method (Section 9.11.2.4), a sensitivity analysis will be conducted by stratifying the PS into five quantiles as an alternative to IPTW and comparing the results. Within each stratum, the effect of treatment on outcomes can be estimated by comparing outcomes directly between tirzepatide and comparator participants. The stratum-specific estimates of treatment effect can then be pooled across stratum to estimate an overall treatment effect.¹⁰⁷ In addition to a truncation method, trimming will be used to assess any influence of excluding extreme weights in a sensitivity analysis.
- Sensitivity analyses will also be conducted to assess the potential impact of missing data and/or unmeasured confounding (e.g., quantitative bias analysis to estimate the overall strength of potential unmeasured confounding required to nullify the estimated treatment effect or reverse the statistical inference).¹⁰⁸
- A sensitivity analysis will be conducted that limits the tirzepatide exposed and the AOM active comparator cohorts to individuals with a diagnosis of obesity, or overweight with at least one weight-related comorbid condition at the time of conception.
- A sensitivity analysis will be conducted that expands the tirzepatide exposed cohort to individuals exposed to any other weight loss medications (including GLP-1 RAs) other than tirzepatide.
- In the main analysis, maternal use of within 5 half-lives of the respective medication is defined as a potential fetal exposure to medication use during pregnancy. This is a conservative estimate which may dilute a potential association between medication and the study outcomes. Sensitivity analysis will be conducted with shorter half-lives (i.e., 1-, 2- and 3-times half-lives) to define fetal exposure to medication use during pregnancy.
- Pregnant individuals who are exposed to a known teratogen or an investigational medication during or prior to pregnancy will be excluded from the main analysis population and described in the supplementary analyses. In the case that there are more than 10% of pregnant individuals with teratogen exposure during or prior to pregnancy, an additional sensitivity analysis will be considered by retaining those individuals in the analysis and addressing potential impact of teratogen exposure via analytical adjustment. More details will be included in the SAP.

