9.9. Study Size

9.9.1. Sample Size

Table 9.4 presents by outcome the sample size (number of live births or pregnant individuals, depending on the outcome) required in each cohort to detect a range of relative risks, from 1.5 to 5.5. Sample size calculations were performed with SAS® statistical software (version 9.4 or higher, SAS Institute, Cary, NC) for the outcomes using the Fisher's exact conditional test with Walters normal approximation method, and assuming a power of 80%, a 2-sided α level of 0.05, an equal number of individuals in each cohort (although other sampling ratios were considered), and observed prevalence of the outcomes in the comparator cohort equivalent to reference rates in the general population. These general population rates were obtained for most (but not all) of the outcomes from various sources, including the Metropolitan Atlanta Congenital Defects Program (MACDP), the National Vital Statistics System (NVSS), and published literature.

Although the registry aims to examine a variety of maternal, fetal, and infant outcomes, the target sample size for the registry is based on the primary outcome, overall prevalence of MCM, which also is the outcome with the most restrictive denominators and one of the lowest prevalence in the general population.

As shown in Table 9.4, 265 live births in the analysis population of each cohort are needed to detect a 3-fold increase in the overall prevalence of MCM between cohorts, or a relative risk of 3.

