total of 1,092 individuals would need to be enrolled in the registry. This sample size will afford the study the ability to detect a 3-fold increase in the overall prevalence of the primary outcome, MCM, in the tirzepatide-exposed cohort, with meaningful confidence (95% confidence level). Additionally, [Table 9.5](#) shows that, without any adjustments for multiple comparisons, the proposed sample size will also afford the study >80% power to detect a 3-fold increase in several of the secondary and exploratory outcomes.

The overall prevalence of MCM is higher among individuals with obesity (BMI >30 kg/m²; 3.9%²⁶) than that of the general population (3%).⁷⁴ However, because it is difficult to estimate the proportion of enrolled individuals who will have obesity at the time of conception (as some will have lost weight prior to conception due to weight management treatment), the more conservative approach assuming an overall prevalence of 3% has been chosen (i.e., the overall sample size calculations were based on the general population prevalence of MCM). Had the higher rate (3.9%) been used, the total sample size for the registry would have been substantially lower (828 vs. 1092). These assumptions also may be re-evaluated after interim analyses have been conducted.

Table 9.4. Sample Size Needed per Cohort to Detect Specific Relative Risk (Exposed: Tirzepatide Unexposed^c)

Outcomes ^a	Reference Prevalence in Unexposed Group	Reference	Denominator of Reference	RR= 1.5	RR= 2.0	RR= 2.5	RR= 3.0	RR= 3.5	RR= 4.0	RR= 4.5	RR= 5.0	RR= 5.5
Primary Objective												
MCM	3.0%	CDC 2008 ⁷⁴	Live births	2,627	796	413	265	190	146	117	97	82
Secondary Objectives												
Pre-eclampsia	3.8%	Ananth 2013 ⁷⁵	Pregnant individuals	2054	622	322	206	148	113	91	75	64
Eclampsia	0.281%	Butwick 2020 ⁷⁶	Live births	28973	8824	4600	2961	2130	1640	1322	1101	940
Gestational diabetes	6.9%	Martin 2021 ⁷⁷	Pregnant individuals	1161	350	180	115	82	62	50	41	35
Pregnancy-induced hypertension	6.5%	Butwick 2020 ⁷⁶	Pregnant individuals	1088	327	169	107	76	58	46	38	32
SAB	11.8%	Wu 2019 ⁷⁸	Pregnant individuals	596	177	90	57	40	30	24	19	16
Stillbirth	0.596%	MacDorman 2015 ⁷⁹	Live births and stillbirths	13610	4142	2159	1389	999	769	619	516	440
Induced abortion	18.6%	Jatlaoui 2019 ⁸⁰	Live births	343	100	50	31	21	15	12	9	NA ^b
Preterm birth	8.47%	Martin 2021 ⁷⁷	Singleton live births	868	260	134	85	60	46	36	30	25
SGA	10.0%	By definition	Live births	721	215	110	70	49	37	29	24	20

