9.11.1.1.7. Multiple Gestation Pregnancies

Multiple gestation pregnancies will be enrolled in the registry and included in the main analysis population; however, for the analyses of preterm birth, SGA, LGA, rapid infant weight gain, postnatal growth deficiency, and infant developmental delay, multiple gestation pregnancies will be excluded from the main analysis population due to the higher risk of these outcomes in twins and higher order multiples.

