9.11.2.1. Analysis of Primary Outcome

Prevalence of the primary outcome will be calculated according to the conventions described in [Table 9.6](#). In general, prevalence will be calculated by dividing the number of cases with an MCM by the appropriate denominator. Prevalence is preferred over incidence when examining pregnancy outcomes, such as congenital malformations, because incidence cannot be reliably estimated given the complexities in the reproductive process.⁹⁷

For MCM, prevalence in the exposed cohort will be calculated among the subset of individuals who are exposed during the first trimester. For the primary analysis, prevalence will be calculated among live births, and a secondary analysis will be conducted among live births and fetal losses ([Table 9.6](#)).

The unweighted univariate regression will be used to compare the crude (unadjusted) relative risks (RRs) of MCM in the tirzepatide exposed and each of the comparator groups, respectively: tirzepatide exposed vs. AOM active comparator and tirzepatide exposed vs. AOM unexposed comparator.

Adjusted methods will incorporate weights estimated using the inverse probability of treatment weighting (IPTW) method to balance the cohorts regarding observable covariates. A weighted generalized linear model using a binomial family and a log (RR) link with robust sandwich variance estimation or a modified Poisson regression⁹⁸ with robust error variance will be employed to estimate an adjusted RR. As with the unweighted analysis, two sets of comparisons will be conducted separately: tirzepatide vs. AOM active comparator and tirzepatide vs. AOM unexposed comparator.

The adjusted comparison of the overall prevalence of MCM observed in the tirzepatide exposed and the comparator cohorts will be considered the primary analysis. A p-value <0.05 will be considered statistically significant.

Table 9.6. Calculation of Primary Outcome Prevalence

Outcome	Numerator	Denominator
Primary analysis: among live births	Live births with confirmed (by adjudication) MCMs (excluding MCMs not known to be associated with medication exposure ^a) among individuals with pregnancy outcome data and, if applicable, exposure during 1 st trimester	Live births among individuals with pregnancy outcome data and, if applicable, ^b exposure during 1 st trimester

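### The convergence reason for leaving sibling correlation unhandled below 10% multiples does not apply to a sandwich variance clustered on the mother, which the MCM analysis could use at no cost

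*Protocol*

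**What the plan says.** - **Who is in.** Protocol 9.11.1.1.7: "Multiple gestation pregnancies will be enrolled in the registry and included in the main analysis population". The same section removes multiples for preterm birth, SGA, LGA, rapid infant weight gain, postnatal growth deficiency and developmental delay. Major and minor malformations are not on that list.
- **Unit of analysis.** Protocol 9.11.2.1: "For the primary analysis, prevalence will be calculated among live births". Table 9.6 uses live births as the denominator, and live births plus fetal losses in the secondary MCM analysis.
- **Variance.** The adjusted MCM model in 9.11.2.1 is a weighted binomial model with a log link "with robust sandwich variance estimation or a modified Poisson regression", the latter with robust error variance. No cluster unit is named. The corresponding paragraph in 9.11.2.2 for the other outcomes names a weighted log-link model and no robust variance.
- **Correlation.** Section 9.11.2.7 adds sensitivity analyses on a condition. For multiples the condition is "if 10% or more have multiple gestation pregnancies". These analyses would "account for the correlation between previous and subsequent pregnancies in the same participant and multiple gestation pregnancies using mixed models". Below the threshold nothing is planned, for the convergence reason: "If percentage is less than 10%, attempting to model the correlation will likely result in a failure of model convergence".

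**The concern.** A twin pair contributes two observations to the MCM model. They share a mother, an exposure history and one propensity weight. A robust variance that sums squared contributions infant by infant treats them as unrelated. If their outcomes are positively correlated, the standard error is too small and the confidence interval for the primary relative risk too narrow.

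The protocol goes beyond leaving this open: it fixes a threshold, a method and a reason. The reason belongs to a different class of model from the one planned for the primary analysis, and it could steer whoever writes the code away from a remedy that carries no such difficulty. What is at stake is the stated precision of the MCM comparison, by a small amount.

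**Working it through.** **1. The plan's own figure.** Inputs from 9.9.1: "assuming a power of 80%, a 2-sided α level of 0.05"; "the more conservative approach assuming an overall prevalence of 3% has been chosen"; relative risk 3, hence 9% in the exposed cohort; 1:1 allocation. With Fisher's exact test under the Walters approximation,

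power = Φ{2√(n/2) · [asin√(p₂ − 1/(2n)) − asin√(p₁ + 1/(2n))] − 1.96}.

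At n = 265, p₁ = 0.03 and p₂ = 0.09 this gives 80.1%, and 265 is the smallest n reaching 80%. Then 265/0.9³ = 363.5, so 364 per cohort and 3 × 364 = 1,092 in total. The 3.9% alternative gives 201 live births, 276 per cohort and 828 in total. All the stated figures reproduce.

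**2. Does clustering add a convergence burden?** The sandwich is A⁻¹BA⁻¹, where A comes from the fitted marginal model and U is each infant's weighted score.
- Per infant: B = Σ U U′ over infants.
- Clustered: B = Σ (ΣU)(ΣU)′, summing U within mother before squaring.

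Both use the same fit, so the relative risk is identical. No variance component is estimated, so there is nothing extra to converge. For a mother with one infant the two terms are equal. With no multiples, the clustered form is the per-infant form.

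**3. Size of the error.** Let t be the share of twin pregnancies and ρ the within-pair correlation of MCM. The protocol gives neither, so both are assumptions. The infant-weighted mean cluster size is m = (1 − t + 4t)/(1 + t), and

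design effect = 1 + (m − 1)ρ = 1 + 2tρ/(1 + t).

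This takes t and ρ as equal in the cohorts compared. The true standard error is √(design effect) times the per-infant one, and the true level of a nominal 5% test is 2[1 − Φ(1.96/√(design effect))].

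| t | ρ | Design effect | SE factor | True level |
|---|---|---|---|---|
| 3% | 0.1 | 1.006 | 1.003 | 0.051 |
| 3% | 0.3 | 1.017 | 1.009 | 0.052 |
| 3% | 0.5 | 1.029 | 1.014 | 0.053 |
| 9.99% | 0.1 | 1.018 | 1.009 | 0.052 |
| 9.99% | 0.3 | 1.054 | 1.027 | 0.056 |
| 9.99% | 0.5 | 1.091 | 1.044 | 0.061 |

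The per-infant standard error is therefore too small by 1 − 1/1.003 ≈ 0.3% up to 1 − 1/1.044 ≈ 4%. The bound ρ = 1 gives design effects of 1.058 (t = 3%) and 1.182 (t = 9.99%), with true levels 0.057 and 0.071.

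**4. Simulation.** Weighted modified Poisson model, 265 pregnancies per arm, 3% risk in both arms, siblings sharing a weight, 3,000 runs per scenario. Rejection rates at the nominal 5% level:

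| t | ρ | Per infant | Clustered |
|---|---|---|---|
| 3% | 0.3 | 0.042 | 0.042 |
| 3% | 1.0 | 0.045 | 0.043 |
| 9.99% | 0.3 | 0.057 | 0.054 |
| 9.99% | 1.0 | 0.063 | 0.051 |

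The Monte Carlo standard error is √(0.05 × 0.95/3000) ≈ 0.004. Of 12,000 runs, 5 had a cohort with no events and were not fitted; every other run converged.

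**The case against.** Four objections deserve weight.

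- **The SAP may settle it.** The protocol never says that infants are treated as independent, and the cluster identifier is a detail often left to the SAP, which was not available here. This stands: it cannot be asserted that the primary interval will be too narrow. It does not rescue the threshold or the reason, which the protocol itself fixes.
- **The convergence sentence is about mixed models.** Read in place, it explains when that sensitivity analysis is run and makes no claim about sandwich variances. That is a fair reading. But it is the only reason the protocol offers for doing nothing below 10%, and it does not cover the simpler option.
- **The harm is hardly visible.** At 3% twins the simulated rates are below nominal under both variances. At 9.99% and ρ = 0.3, 0.057 is within two Monte Carlo standard errors of 0.05. Clear inflation needs ρ = 1 just under the trigger. This stands and limits the point to a minor one.
- **Correlation may be low.** The MCM definition removes chromosomal, genetic, prematurity-related and crowding-related findings, so some shared causes within a pair are already gone. This also stands. Number of fetuses as a potential covariate (9.7.4) would not help, since it addresses mean risk and not correlation.

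A reader might also infer that the mixed model would change the estimand. The documents do not support that. The outcome models in 9.11.2.1 and 9.11.2.2 use a log link, and 9.11.2.7 names no other. With a log link and a random intercept independent of exposure, E[exp(a + bx + u)] = exp(a + bx) · E[exp(u)]. Only the intercept moves and the relative risk is the same. A difference would arise with a logit link, which the protocol does not mention.

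**Conclusion.** The point holds as a minor, free improvement. The protocol keeps multiples in a per-infant primary analysis, names no cluster unit, and justifies inaction below 10% by a difficulty that a mother-clustered sandwich does not have. The standard error would be about 0.3% to 4% too small, conditional on positive within-pair correlation, a variance computed per infant, and the assumed ranges t = 3% to 10% and ρ = 0.1 to 0.5.

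Three wider readings are not supported:
- The 10% trigger does not repair the primary analysis. It only adds a sensitivity analysis.
- Infant outcomes in general are not affected. In the main analysis only major and minor malformations retain multiples, and subsequent pregnancies are excluded from it (9.11.1.1.6).
- The sample size is not in error. The figures 265, 364 and 1,092 are unaffected.

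**What to change.** - **9.11.2.1:** state that the robust variance is clustered on the pregnant individual in the MCM models, whatever the share of multiples.
- **9.11.2.2:** for minor malformations, state a robust variance, since none is named there, and cluster it in the same way.
- **9.11.2.7:** drop the 10% convergence condition for this purpose, and use the same clustered marginal model when subsequent pregnancies or multiples are added to an analysis.

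The cost is one identifier in the variance statement and a few words of text. Point estimates, sample size and data collection do not change. If the SAP already clusters on the mother, only the protocol wording needs to be aligned with it.

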9.11.2.8. Missing Data

For critical data points, missing values are expected to be minimal, thereby negating the need for imputation. As is described in Section 9.6.1, the registry will make multiple attempts to obtain missing data for critical data points. The frequency and percentage of participants with missing data for each data point will be presented.

For start and end dates of medical conditions or exposures, if the month and year are known but the day is missing, then the day will be imputed for analyses: missing start dates will be set to the first day of the month, and missing end dates will be set to the last day of the month. Listings will continue to present the day as missing.

If there is a high degree of missing covariate data ($\geq 10\%$), multiple imputation may be considered to minimize the loss of observations in the analysis by creating the set of weights for each imputed dataset and then averaging them into a single treatment effect estimate.^{104,105}

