9.6.3. Awareness and Retention

9.6.3.1. Awareness Strategy

An active, targeted, multi-pronged awareness campaign will be employed to recruit participants for the registry. The campaign will focus on:

- Pregnant individuals
- Individuals who have a diagnosis of obesity or overweight with at least one weight-related comorbid condition
- Individuals using tirzepatide or other products for weight management
- Obstetric HCPs
- HCPs who are likely to treat patients with diagnoses of obesity or overweight with at least one weight-related comorbid condition
- HCPs who are likely to prescribe tirzepatide or other products for weight management (including, but not limited to, other therapies with GLP-1 RA activity).

As described in Section 7.4.1, non-Hispanic black and Hispanic individuals are at an increased risk of pre-pregnancy obesity compared to non-Hispanic white and Asian individuals; therefore, the sponsor will make efforts to improve enrollment of participants from underrepresented racial and ethnic populations in this study.

Obstetric HCPs and HCPs who are likely to treat patients with obesity may be identified via HCP directories and/or professional associations. If appropriate and/or needed, pregnant individuals, patients who have a diagnosis of obesity or overweight with at least one weight-related comorbidity, and patients using tirzepatide may be identified through patient support groups and external data sources, such as pharmacy/medical claims or electronic medical records. If appropriate, the sponsor's existing infrastructure for distributing tirzepatide and supporting stakeholders may be leveraged to identify HCPs who are known to prescribe tirzepatide and pregnant individuals who have been exposed to tirzepatide.

To start, the primary aim of the registry's awareness strategy will be to recruit individuals exposed to tirzepatide during pregnancy. Once the characteristics of a portion of the tirzepatide-exposed participants are understood, the awareness campaign for the comparator cohort will be tailored to increase comparability of the cohorts. In addition, individuals who were exposed to tirzepatide before (>25 days prior to date of conception [DOC]) but not during pregnancy (<25 days prior to DOC to pregnancy outcome) will be targeted for enrollment into the comparator cohort.

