9.7. Variables

9.7.1. Exposure Definitions and Ascertainment

Exposure to tirzepatide is a condition for inclusion into the exposed cohort. Exposure is defined as bodily uptake of any dose of tirzepatide at any time during pregnancy (from conception to pregnancy outcome) or prior to pregnancy (within a specified time based on the product's half-life). Due to the half-life of tirzepatide (approximately 5 days), tirzepatide is likely to be eliminated from the body within 5 half-lives (25 days or 3.5 weeks). Therefore, individuals exposed to tirzepatide within ≤ 25 days of DOC will be considered exposed. Individuals in the tirzepatide cohort who are exposed to other GLP-1 RA therapies during pregnancy or within 5 times the half-life of the drug prior to conception will be excluded from the main analysis to prevent class effect interactions. However, they may still be enrolled into the study as part of the tirzepatide exposed cohort.

Exposure to comparator products for weight management is defined as bodily uptake of any dose of a qualifying product for weight management at any time during pregnancy (from conception to pregnancy outcome) or prior to pregnancy (within 5-half-lives of DOC). Detailed information on drugs for weight management and their respective exposure windows are detailed in Drugs of Interest for Cohort Eligibility.

Detailed information on dose, route, frequency, dates/duration of exposure, and indication/reason for use will be collected, and exposure will be further categorized by earliest trimester of exposure. Section 9.7.5 provides information on the methods used to determine gestational age and trimester of exposure.

Exposure information will be updated at each pregnancy follow-up and changing exposures will be accounted for in the analysis. For example, if a pregnant individual was enrolled into the comparator cohort but later during pregnancy became exposed to tirzepatide, for the analysis they would be included in the tirzepatide exposed cohort.

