DOC, defined as 2^{0/7} gestational weeks, will be calculated as first day of LMP plus 14 days (2 weeks).

If EDD is not reported by the HCP but LMP data are available, the registry will use first day of LMP to calculate EDD, gestational age, and DOC.

Individuals will be considered exposed during pregnancy if the exposure occurs any time from 25 days prior to the DOC to the pregnancy outcome. For the analysis of MCM, first trimester exposure will be defined as exposure from 5 times the product's half-life (i.e., 25 days for tirzepatide) prior to the DOC to 13^{6/7} gestational weeks.

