- Concurrent pregnancy-related maternal medical conditions or pregnancy complications, including
 - Preterm labor
 - Placenta previa
 - Placental abruption
 - Incompetent cervix
 - Ectopic pregnancy
 - Molar pregnancy

Maternal Exposures during Pregnancy

Collected from HCP(s) – obstetric and prescriber, if needed – at enrollment, end of 2nd trimester, and pregnancy outcome; at the end of the 2nd trimester and pregnancy outcome, HCPs are asked only for updates to the data previously reported

- Exposure to tirzepatide, including indication/reason for use (approved according to label in country of residence), dose, route, frequency, and dates/duration of exposure, if available
- Exposure to other drugs or biological products (including prescription and non-prescription drugs, dietary/herbal supplements (including folic acid and prenatal vitamins), vaccines (including COVID-19), known teratogens (see Section 9.11.1.1.4), and investigational medications), including indication/reason for use, dose, route, frequency, and dates/duration of exposure, if available
- Exposure to tobacco, alcohol, marijuana, or recreational or illicit drugs, including timing of exposure, if available

Pregnancy Outcome Information

Collected from HCP(s) – obstetric and pediatric, if needed – at or after pregnancy outcome

- Pregnancy outcome (for each fetus, classified in one of the following mutually exclusive categories: SAB, stillbirth, induced abortion, and live birth)
- Maternal outcomes: pregnancy induced hypertension, pre-eclampsia, eclampsia, gestational diabetes, maternal cardiac disease, HG, and inadequate GWG.
- Date of pregnancy outcome
- Gestational age at pregnancy outcome
- Fetal/infant sex
- Fetal/infant weight, length, and head circumference at pregnancy outcome (when available)
- Labor type (spontaneous or induced)
- Route of delivery (i.e., vaginal delivery, assisted vaginal delivery, planned caesarean delivery, or emergency caesarean delivery)
- Delivery complications
- 5 Apgar scores
- Congenital malformations (major and minor), including post-mortem findings for fetal losses and assessment of potential contributing factors
- Maternal weight at (just prior to) pregnancy outcome
- For live births, prolonged hospitalization after delivery and reason
- For a non-induced fetal loss (SAB, stillbirth), factors that may have had an impact on the fetal loss and attribution

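### For past tirzepatide users whose stop day stays unknown, month-end imputation can stretch the 25-day pre-conception window to as much as 55 days, always toward exposed

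*Protocol*

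**What the plan says.** Section 9.11.2.8 (Missing Data) gives a fixed rule. Its scope is stated as "For start and end dates of medical conditions or exposures", its trigger is "if the month and year are known but the day is missing", and its action for stop dates is that "missing end dates will be set to the last day of the month". Missing start days go to the first of the month. The imputed day is used in analyses, while listings keep it as missing.

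Cohort membership depends on a date. Section 9.7.1 says "individuals exposed to tirzepatide within ≤ 25 days of DOC will be considered exposed", and section 9.7.5 says "Individuals will be considered exposed during pregnancy if the exposure occurs any time from 25 days prior to the DOC to the pregnancy outcome". Section 9.6.3.1 states that women who took tirzepatide more than 25 days before conception, but not later, "will be targeted for enrollment into the comparator cohort".

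Section 9.8 collects tirzepatide "dates/duration of exposure, if available". Section 9.6.2 treats exposure as a critical data point: the healthcare provider is queried, with three further attempts if needed. Section 9.11.2.8 expects little missing critical data but gives no rate.

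**The concern.** The classification boundary is 25 days wide, and the imputation can move a stop date by more than that. For stop dates it moves in one direction only. A woman who is exposed on her true date stays exposed, whereas a woman just outside the window can be moved in. The registry deliberately recruits past users as comparators, so it enrols the group in which this can happen.

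An example: conception is on 10 April, so the window opens on 16 March. The record says only that tirzepatide stopped in March. If the last dose was on 1 March, the true gap is 40 days and she is unexposed. The rule records 31 March, a gap of 10 days, and she is analysed as exposed.

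If such women enter the exposed cohort, their background malformation risk dilutes any true increase. In a safety study, that is the direction that can hide harm. Section 9.11.2.7 already concedes that the five-half-life window may dilute an association, but it does not mention that imputation can widen that window.

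**Working it through.** **Inputs.** Window of 25 days (9.7.1, 9.7.5). Month-end rule (9.11.2.8). Reference malformation prevalence 3%, relative risk 3, 265 live births per cohort, 80% power, two-sided alpha 0.05, Fisher's exact test with Walters approximation (9.9.1). Assumptions not in the protocol: the true stop day is uniform over a 365-day year, and the misclassed share f takes illustrative values.

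**1. The plan's own figure.** With n per cohort, power = Φ(√(2n)·[arcsin√(p₂ − 1/(2n)) − arcsin√(p₁ + 1/(2n))] − 1.96). For n = 265, p₁ = 0.03 and p₂ = 0.09, power is 80.1%, and 265 is the smallest n reaching 80%. Enrolment is 265/0.9³ = 363.5, so 364 per cohort and 1,092 in all. The stated figures are reproduced.

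**2. Size of the shift.** Shift = last day of month − true day. It runs from 0 to 30 days in 31-day months, 0 to 29 in 30-day months and 0 to 27 in a 28-day February. The mean is 14.7 days. It is never negative, and it exceeds 25 days for 14.5% of possible stop days (53/365). The longest effective window is 25 + 30 = 55 days.

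**3. Chance of being classed as exposed, day missing, true gap g > 25 days.** This is P(shift ≥ g − 25). For k = g − 25 up to 28 it equals (365 − 12k)/365; at k = 30 only the seven 31-day months contribute, giving 7/365.

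| True gap (days) | Classed as exposed |
|---|---|
| 26 | 353/365 = 97% |
| 30 | 305/365 = 84% |
| 35 | 245/365 = 67% |
| 40 | 185/365 = 51% |
| 45 | 125/365 = 34% |
| 50 | 65/365 = 18% |
| 55 | 7/365 = 2% |
| 56 or more | 0% |

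The average over gaps of 26 to 55 days is 14.72/30 = 49%.

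**4. Do the planned shorter windows deal with it?** Section 9.11.2.7 repeats the analysis with 1, 2 and 3 half-lives, which for tirzepatide is 5, 10 and 15 days. If these use the same imputed dates, a true gap of 26 days is still classed as exposed with probability 31% (113/365), 47% (173/365) and 64% (233/365) respectively. The error is reduced but not removed.

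**5. Effect on the primary comparison.** If a share f of the exposed cohort is truly unexposed, observed RR = 1 + (3 − 1)(1 − f). Power comes from step 1 with p₂ = 0.03 × observed RR and n = 265.

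| Assumed f | Observed RR | Power |
|---|---|---|
| 0 | 3.00 | 80% |
| 2% | 2.96 | 79% |
| 5% | 2.90 | 77% |
| 10% | 2.80 | 73% |
| 20% | 2.60 | 63% |

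**6. Other classifications under the same rule.** A start date moved to the first of the month can turn a second-trimester start into first-trimester exposure, which decides entry to the malformation analysis (9.7.5, 9.11.2.1). A stretched stop date for a teratogen can exclude a pregnancy; for short half-life agents the pre-conception window is only the 14 days from last menstrual period to conception. A stretched stop date for another GLP-1 receptor agonist can remove a truly tirzepatide-exposed woman from the main analysis (9.11.1.1).

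**The case against.** The strongest reply is that the rule may rarely, or never, decide a cohort. Section 9.11.1.1.1 requires enough data, submitted or confirmed by a provider, to assign the cohort, and drops participants who lack it. Section 9.6.2 adds queries and then a documented determination by registry staff or the investigator. On that reading, unresolved dates are settled or removed before imputation is reached. This stands as a reason to expect few cases. It does not override the rule: neither section says that a month and year without a day is insufficient data, and 9.11.2.8 covers exposure dates used in analyses without exemption.

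The group at risk is also narrow. Section 9.6.3.1 sets no upper limit on how long ago past users stopped, so many will be beyond 55 days. Women who stop only when pregnancy is recognized, as section 7.4.3 says they are advised to do, have a true stop after conception and remain exposed under month-end imputation. Both points stand.

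A reader might infer that unexposed pregnancies in general are systematically classed as exposed. The documents do not support that. A never-user has no stop date. Four things must coincide: past use, a stop day still missing after queries, a true last dose 26 to 55 days before conception, and a month-end that falls inside the window. What is systematic is the direction of the error among those women.

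Finally, widest-interval imputation is defensible in a design that defines exposure broadly, and the SAP, which is not at hand, may add detail. But the protocol has fixed the rule, and neither its shorter-window analyses nor its unspecified missing-data sensitivity analysis is stated to vary the imputed day.

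**Conclusion.** The point holds in limited form. For past tirzepatide users with a known stop month and an unresolved stop day, the rule lengthens the 25-day window to as much as 55 days and moves women only into the exposed cohort. The resulting bias in the tirzepatide comparison is toward a relative risk of 1.

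The 97%, 51% and 49% figures are conditional on a missing day and on a gap in the affected range, and they assume a uniform stop day. They should not be read as shares of any cohort. The actual share cannot be derived from the protocol and is likely small. At an assumed 5%, the loss is 0.10 in the relative risk and between three and four percentage points of power. For the teratogen and other GLP-1 exclusions the rule removes pregnancies instead of adding them, so its net effect on the relative risk through those routes is not established. The change is worth making because it is cheap and the error runs toward missing harm.

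**What to change.** Amend section 9.11.2.8 as follows:

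- Where the earliest and the latest possible day in the recorded month give the same classification, use that classification.
- Where they differ for cohort membership, first-trimester status, or an exclusion for teratogens or other GLP-1 receptor agonists, flag the pregnancy as indeterminate and report the number flagged by cohort.
- Repeat the primary malformation analysis under the earliest-day and under the latest-day classification.
- Keep first-day and last-day imputation for descriptive durations.

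Bounding the result in this way is preferable to dropping indeterminate pregnancies from the main analysis, which is more debatable. The cost is a wording change and modest programming, with no new data collection.
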